## 5 STUDY TREATMENTS

### 5.1 INVESTIGATIONAL MEDICINAL PRODUCTS

The patient will be trained for the correct instillation technique of IMP by the **unmasked team member**. The patient will be provided with a patient's study guide.

#### 5.1.1 Test Product: T4090

The IMP T4090 is a PF eye drops solution presented in SDC filled to 0.2 mL. T4090 0.2% and 0.3% solutions are prepared according to the formula's details in investigator's brochure.

Component	Formula (g/100 mL)		Function(s)	Reference to standards
	T4090 0.2%	T4090 0.3%		
Kinezodianone R hydrochloride	██████████	██████████	Drug substance	Internal Method

A single dose contains enough eye drop solution to treat both eyes. For single use only.

The excipients of the T4090 eye-drops ██████████

Batch number and retest dates will be provided in the certificate of analysis.

#### 5.1.2 Control Product: Rhopressa

Rhopressa (0.02% netarsudil) ophthalmic solution is supplied sterile in opaque white low density polyethylene MDC and tips with white polypropylene caps in 2.5 mL fill in a 4 mL container.

RHOPRESSA	Formula (mg / mL)
Active ingredient	
Netarsudil dimesylate	0.2
Benzalkonium chloride	0.015%
Boric acid,	
Mannitol,	
Sodium hydroxide	

Batch number and expiration dates will be provided.

#### 5.1.3 Packaging, Labelling and Storage

T4090 will be manufactured by Unither Coutances (██████████) in accordance with the European Union (EU) Good Manufacturing Practices (GMP), including the EU GMP Annex 13.

Rhopressa will be obtained from commercial batches.

The IMPs will be packaged by approved contractor in accordance with GMP. The IMPs will be prepared according to a packaging list.

The IMPs will be prepared according to the randomization list provided by the statistician.

### 5.1.3.1 Packaging

Each treatment unit, *i.e.*, the complete treatment for one patient and for the complete study duration will be as following.

Packaging	T4090 0.2% 0.3%	Rhopressa	T4090 0.2% 0.3%	Rhopressa	T4090 0.2% 0.3%	Rhopressa
	Day 1 to Week 2		Week 2 to Week 4		Week 4 to Week 7	
Primary	20 SDC	1 MDC	20 SDC	1 MDC	30 SDC	2 MDC
Secondary	2 aluminum pouches	1 final cardboard carton	2 aluminum pouches	1 final cardboard carton	3 aluminum pouches	1 final cardboard carton
			1 final cardboard carton		1 final cardboard carton	

MDC=multiple-dose container; SDC=single-dose container

### 5.1.3.2 Labelling

All labels will be written in the local language. The content of the labelling is in accordance with specifications, regulations, and local requirements (21 CFR312 for US).

Each SDC/MDC/aluminum pouch/ cardboard carton will carry one label.

The cardboard carton will also carry a detachable label (flag label) bearing at least the protocol number and IMP number. This label will be torn off by the person dispensing the IMP to the patient and will be stuck in the patient unmasked source document to record the dispensing procedure.

### 5.1.3.3 Storage

#### T4090

T4090 must be stored in the original packaging (aluminum pouches), protected from light in cardboard carton at [REDACTED] and should not be used after the expiry date indicated on the outer cardboard box.

#### Rhopressa

Rhopressa must be store at 2°C to 8°C (36°F to 46°F) until opening.

After opening, the product may be kept at 2°C to 25°C (36°F to 77°F) for up to 6 weeks.

If after opening, the product is kept refrigerated at 2°C to 8°C (36°F to 46°F), then the product can be used until the expiration date stamped on the MDC. During shipment, the MDC may be maintained at temperatures up to 40°C (104°F) for a period not exceeding 14 days.

Until dispensed to the patient, products must be in a secure area with restricted access. The unmasked team, the hospital pharmacist or other personnel allowed to store and dispense IMP(s) will be responsible for ensuring that the IMP(s) are securely maintained as specified by the Sponsor and in accordance with the applicable regulatory requirements.

If significant changes and/or update on labelling, handling and storage are required during the study, the corresponding sections will be updated by notifying or submitting to Competent Authorities concerned

accordingly. All investigator sites will be immediately informed about any change by the Sponsor. investigator or a delegate will inform the patient, if any.

Accordingly, the Sponsor may decide to halt temporary the recruitment (see [Section 8.7](#)). In any way, the reasons and the procedures for any changes will be justified and described by the Sponsor.

### **5.1.4 Masking and Code Breaking**

This will be an investigator-masked clinical study. To respect this constraint, a masked and unmasked teams will be assigned. The role and responsibilities of masked and unmasked site staff will be further described in the delegation of function log.

#### **Masking**

The **masked investigator/designee**, in charge of ophthalmic examinations (including IOP measurement) are not aware of the allocated treatment (T4090 or Rhopressa).

At the end of the IMP masking period, the masked investigator will confirm in the e-CRF that she/he has not been unmasked during the study.

Each site must have at least one **unmasked team member** dedicated to IMP management (e.g., Unmasked Investigator and /or Pharmacist or other qualified site staff per local regulation).

Only **unmasked team members** are permitted to manage IMP once received on site from Depot. The study IMP must be stored in a secure location.

The IMP will be delivered by the **unmasked team member**.

The **unmasked team member** will explain to the patient how to use the IMP and how to complete the patient daily diary.

This **unmasked team member** does not participate in the evaluation of patients (ophthalmic examinations, including IOP measurement), after first IMP dispensation and does not communicate any unmasking information with the masked teams.

The IMP will be returned by the patient to the **unmasked team member**.

The **unmasked team member** will be in charge for verifying compliance by checking IMP returns, the patient's diary information and by patient's interview. Information regarding compliance will be shared with the **masked investigator/designee** employing a masked approach (*i.e.*, without revealing treatment allocation or type of IP). The unmasked staff cannot help for any blinded procedures such as EDC entry.

Patients will be instructed not to discuss IMP with the **masked investigator/designee**.

All documents that could contain unmasking information must be kept separate from the masked site staff.

**Masking** will be achieved by providing each product unit with identical cardboard carton (same final packaging, same weight, and dividers to avoid boxes or aluminum pouch to move) and by identifying it by an IMP number.

#### **Code breaking**

The code should not be broken except:

- in case of medical emergency (where knowledge of the IMP received would affect the treatment of the emergency)
- or when it is a regulatory requirement (e.g., for Suspected Unexpected Serious Adverse Reactions [SUSARs]).

The masked investigator/designee is responsible for accessing the IRT System to obtain the identity of the IMP received by the patient. If an emergency code breaking becomes necessary, the investigator should notify the Sponsor, if possible, prior to breaking the code.

When a code is broken, the date, time and reason must be recorded in the IRT as well as in the patient's source documentation, and in any associated AE report. The identity of the IMP **should not be** disclosed in these documents.

Further to a SUSARs assessment by the Global Drug Safety & Medical Information Department, the code might be broken for reporting purposes. The relevant Laboratoires THÉA, CRO and masked investigator and masked staff remain unaware of the identification of the IMP as per the above-mentioned process.

The Sponsor's collaborators responsible for the data medical evaluation will remain masked.

The overall randomization list will be broken for data analysis after database lock.

## 5.1.5 Dispensing and Return

### 5.1.5.1 Dispensing

The IMPs must be dispensed only to patient in accordance with the protocol and the randomization.

At the Randomization visit (D1), once selection criteria have been checked and once the patient is eligible, the randomization will be performed, and an IMP number will be allocated to the patient.

IMP will be delivered by the **unmasked team member**. Each IMP dispensation will be recorded in the related unmasked documentation.

During the whole study treatment period, the **masked investigator** will remain masked to the IMP (T4090 or Rhopressa). He/she will not deliver or receive the returned medication from the patient and will be trained not to discuss IMP with patients.

All information regarding the usage of the IMPs will be given to patients and will be explained by the **unmasked investigator**.

During the study, three deliveries will be performed as follow:

- At Randomization visit (D1): one box containing enough medication for the treatment period D1 to W2 with the daily diary associated to this period will be provided to the patient by the **unmasked team member** with the number assigned by the IRT
- Visit #3 – W2: resupply of one box containing enough medication for the treatment period W2 to W4 with the daily diary associated to this period, will be provided to the patient by the **unmasked team member** with the number assigned by the IRT
- At Visit #4 - W4: resupply of one box containing enough medication for the treatment period W7 with the daily diary associated to this period, will be provided to the patient by the **unmasked team member** with the number assigned by the IRT.

A record of the IMP dispensed to the patient will be maintained by the **unmasked team member** in the patient unmasked medical records and the accountability log.

The **unmasked team member** will instruct patients not to discuss IMP with the **masked investigator** and on method of instilling the doses:

- Treatment period: IMP (T4090 or Rhopressa) will be instilled by the patient one drop in each eye once daily at 8:00 PM ( $\pm 1$  h).

This is crucial to maintain the blind and avoid any accidental unmasking.

### 5.1.5.2 Return

Patient will return used and unused IMPs in the original packaging and the diaries to the site at each visit (Visit #3, Visit #4 and Visit #5).

The **unmasked team member** counts the number of IMP remaining in the returned pack, completes and validates the accountability log (used, not used, not returned IMP). In addition to returned IMP, he/she questions the patient on the IMP compliance (number of missing doses, if any, modification of instillation time) compares with the information reported by the patient in the daily diary and records the details in the unmasked file.

The **masked investigator will remain masked to the IMP (T4090 or Rhopressa). He/she will not deliver and retrieve the product to any patient** and is not allowed to see the IMP documentation (acknowledgement of receipt product, accountability log). All IMP and IMP documents should be stored in a secured locked area.

All study products will be retained for reconciliation by the unmasked study monitor. The unmasked monitor will, upon completion and validation of drug accountability, returned IMP to depot as instructed by Laboratoires THÉA.

## 5.2 PRIOR AND CONCOMITANT MEDICATIONS

Previous and concomitant treatments have to be recorded on the patient medical record and on the e-CRF documenting product details, dose regimen and intake dates. Concomitant treatment means any medications or non-medicinal therapies given concurrently with the IMP. Any other local or systemic treatment necessary for the patient's welfare has also to be recorded on the patient medical record and on the e-CRF documenting product details, dose, and treatment duration.

### 5.2.1 Prohibited Prior and Concomitant Medications or Treatments

#### 5.2.1.1 Prohibited Treatments

Prohibited treatments as well as prohibited modifications during the study are presented in the summary in the exclusion criteria and are further detailed in this section.

The prohibited treatments (or prohibited modifications of a treatment regimen) and their periods of use prohibition are listed [Table 3](#).

## 6 STUDY CONDUCT

### **Preliminary remark: Informed consent**

Before informed consent may be obtained, the investigator should provide the patient ample time and opportunity to inquire about details of the study and to decide whether or not to participate in the study. All questions about the study should be answered to the satisfaction of the patient. The patient must be given the opportunity to ask questions and have reasonable time for reflection before giving his/her informed consent.

Written informed consent must be obtained prior to initiation of any study procedures or any discontinuation of current medication.

No measures whatsoever described in the study protocol shall be undertaken without such consent indicating that the patient has been given both verbal and written information about the study and the IMP.

The informed consent form both in paper shall be signed and dated by the patient and the investigator or his/her designee. The person who obtained the consent must be suitably qualified and experienced and have been authorized to do so by the Investigator. A copy of each signed consent form must be provided to the patient. All the original signed and dated consent forms must remain in each patient's study file or in the site file and must be available for verification by study monitors at any time.

[figure not shown]
The ICF signature by both parts (including ICF version) should be documented in the patient medical record.

After informed consent has been obtained, the patient will be allocated a patient identifier and evaluated to determine study eligibility.

### **6.1 SCHEDULE OF VISITS**

The schedule of visits, including the timing of examinations and assessments is presented in [Table 4](#).

The following procedures and examinations **must respect the delegation of functions log**:

- done according to local law/regulations
- defined to maintain the masking
- documented and filed in the ISF.

### 6.1.1 Screening period

#### Visit #1: Screening visit

Visit #1 will consist of the following procedures and examinations to be done according to the following order and in each eye.

- Time of the measurements will be recorded
- Information of the patient and signature of the informed consent must be obtained by the patient and the investigator prior to initiation of any study-specific procedures (can be done before this visit)
- Demography
- History of the glaucoma or OHT
- Questioning about ocular medical and surgical history other than the studied disease
- Questioning about systemic medical and surgical history
- Questioning about previous and concomitant ocular and non-ocular treatments (including contraception, if applicable)
- Measurement of far BCVA
- Automated visual field (if not done in the 3 previous months and/or results not available). In case visual field would have to be performed at Visit# 5 or premature treatment discontinuation Visit the same type of device and the same program must be used
- Slit lamp examination for measuring:
  - Measurement of conjunctival hyperemia with [REDACTED] photographic scale
  - Score of each ocular sign
  - Anterior chamber examination for assessing Tyndall effect
  - Conjunctival staining with [REDACTED] grid (lissamine green staining)
  - Corneal staining with [REDACTED] grid scheme (fluorescein staining)
- Fundus examination
- **IOP Measurements performed at 8:00 AM ( $\pm 30$  min)**
- Corneal thickness measurement
- CEC assessments
- Gonioscopy
- Questioning about AEs
- Verification of inclusion and exclusion criteria
- Patient card dispensation
- Status of the patient.

The investigator must ensure that there is no interaction between the exams respecting sufficient time between them.

**Naïve patients** may be randomized the same day as screening visit under the following condition:

- IOP measurements should be done at 8:00 AM, 10:00 AM, 4:00 PM ( $\pm 30$  min) with AM measurements of IOP at least 1.5 (90 min) hours apart in order to check IOP eligibility criteria and the Visit#1 will be recorded as the Randomization visit (Visit #2, D1).
- IOP measurements should be done by the **same masked investigator/designee** and using the same calibrated Goldmann applanation tonometer at all other visits.

If it's not possible to randomize the patient the same day, the Randomization visit must be scheduled within a maximum of 14 days.

**Patients using ocular hypotensive medication** before Screening visit

Instructions will be given to the patient. The patient must be willing to discontinue their current antiglaucoma treatment for the specified washout period prior to Visit #2 (D1), in order to determine their IOP eligibility.

The next visit must be scheduled no later than 8:00 AM ( $\pm 30$  min) between a minimum of 4 day and a maximum of 31 days (according to the previous antiglaucoma treatment) after Visit #1.

**During the washout period, the patient may attend the following visits:**

**Optional Visit #1.1:** Optional visit planned according to the investigator's judgement at any time during the washout period for intraocular pressure (IOP) monitoring:

Visit #1.1 will consist of the following procedures and examinations:

- Time of the measurement will be recorded
- Questioning about AE and previous/concomitant treatments will be done
- According to IOP assessment and investigator judgement:
  - Patient will continue the washout period until Visit #1.2

OR

- Patient will be withdrawn from the study and the investigator will ensure the continuity of antiglaucoma medication as per routine clinical practice.

**Visit #1.2**

Patients will be required to visit the investigators site and have their IOP measurement taken at 8:00 AM after the washout period defined by the previous treatment (from 5 days to 28 days).

Visit #2 will consist of the following procedures and examinations to be done according to the following order and in each eye by **respecting the delegation of functions defined to maintain the masking**

- Time of the measurement will be recorded
- Questioning about AE and previous/concomitant treatments will be done
- **IOP Measurements performed at 8:00 AM ( $\pm 30$  min) IOP have to be performed by the masked investigator**
  - If the investigator considers the washout period as sufficient (the baseline IOP meets the entry requirement), the visit will be recorded as the **Randomization visit** (Visit #2, D1)

OR

- If the investigator considers the washout period as incomplete (the baseline IOP does not meet the entry requirement) and decide to extend the washout period of the patient (up to a maximum of 7 days), the visit will be recorded as the **Visit #1.2**.

If the patient is withdrawn from the study, the investigator will ensure the continuity of antiglaucoma medication as per routine clinical practice.

### 6.1.2 Treatment Period

**Examinations and questionnaires marked with a (\*) MUST be performed by the SAME masked investigator for who performed the assessment at the Randomization visit**

#### Visit #2: *Randomization visit (D1)*

Visit #2 will consist of the following procedures and examinations to be done according to the following order and in each eye by **respecting the delegation of functions defined to maintain the masking**

- Time of the measurements will be recorded.
- **Questioning about previous and concomitant ocular and non-ocular treatments\***
- **Questioning about ocular symptoms\***
- **Measurement of far BCVA\***
- **Slit lamp examination** will be done, by the **same masked investigator/designee** for all following visits, for measuring in each eye\*:
  - **Measurement of conjunctival hyperemia with [REDACTED] photographic scale**
  - **Score of each ocular sign**
  - **Anterior chamber examination for assessing Tyndall effect**
  - **Conjunctival staining with [REDACTED] grid (lissamine green staining)**
  - **Corneal staining with [REDACTED] grid scheme (fluorescein staining)**
- **IOP Measurements\*** at 8:00 AM, 10:00 AM and 4:00 PM (each ±30 min) with AM measurements of IOP at least 1.5 (90 min) hours apart. For each timepoint, measurements of IOP have to be performed by the **same masked investigator** using the same calibrated Goldmann applanation tonometer. A staff member will read and transcribe the IOP values (readout of the tonometer).
- CEC assessments with images:
  - Central photographs will be performed in each eye
  - Anonymized photos will be collected for central reading
- **Questioning about AE\***
- Urine pregnancy test (if applicable) (to be done at any time during the visit)
- Verification of inclusion and exclusion criteria
- Status of the patient: inclusion or screen failure indicating the main criteria not met
- **Randomization (IRT) and IMP prescription according to allocated IMP number\*.**

**By the unmasked team member:**

- IMP dispensation according to allocated IMP number for 2 weeks given explanations to the patient on how and when to use the IMP
- Patient daily diary dispensation and given explanations to the patient on how to complete the diary
- Given instructions to bring back all IMP (used and not used) in their original package and the completed daily diary at the next visit to an unmasked team and not the masked investigator.
- Given instruction not to share any information on the IMP with the **masked investigator**

The next visit must be scheduled on the appropriate day (Day 15±2 days) with IOP measurement at 8:00 AM (±30 min).

**Visit #3 –W2 - Day 15 (±2 days)**

Visit #3 will consist of the following procedures and examinations to be done according to the following order and in each eye by respecting the delegation of functions defined to maintain the masking.

**By the unmasked team member:**

The **unmasked team member** counts the number of IMP remaining in the returned pack, completes and validates the accountability log (used, not used, not returned IMP). In addition to returned IMP, he/she questions the patient on the IMP compliance (number of missing doses, if any, modification of instillation time) compares with the information reported by the patient in the daily diary and records the details in the unmasked file. Information of compliance will be shared with masked investigator/designee employing a masked approach.

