**By the masked investigator/designee for selected tasks (the same as at the Randomization visit):**

- Time of the measurements will be recorded.
- **Questioning about concomitant ocular and non-ocular treatments\***
- **Questioning about ocular symptoms immediately after drop instillation\***
- **Questioning about ocular symptoms throughout the day\***
- **Measurement of far BCVA\***
- **Slit lamp examination** will be done, by the same masked investigator as Randomization visit for measuring in each eye \*:
  - **Measurement of conjunctival hyperemia with [REDACTED] photographic scale**
  - **Score of each ocular sign**
  - **Anterior chamber examination for assessing Tyndall effect**
  - **Conjunctival staining with [REDACTED] grid (lissamine green staining)**
  - **Corneal staining with [REDACTED] grid scheme (fluorescein staining)**
- Fundus examination in both eyes if the investigator judges that it is necessary
- **IOP Measurements\*** at 8:00 AM, 10:00 AM and 4:00 PM (each ±30 min) with AM measurements of IOP at least 1.5 (90 min) hours apart. For each timepoint, measurements of IOP have to be performed **by the same masked investigator** using the same calibrated Goldmann applanation tonometer as Randomization visit. A staff member will read and transcribe the IOP values (readout of the tonometer).
- **Questioning about AE\***
- **Assessment of the efficacy and the ocular tolerance by the investigator\***

- **Assessment of the ocular tolerance by the patient\***
- Status of the patient
- IMP prescription according to allocated IMP number (IRT).

The next visit must be scheduled on the appropriate day (Day 29±3 days) with IOP measurement at 8:00 AM (±30 min).

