**By the unmasked team member:**

The **unmasked team member** counts the number of IMP remaining in the returned pack, completes and validates the accountability log (used, not used, not returned IMP). In addition to returned IMP, he/she questions the patient on the IMP compliance (number of missing doses, if any, modification of instillation time) compares with the information reported by the patient in the daily diary and records the details in the unmasked file. Information of compliance will be shared with **masked investigator/designee** employing a masked approach.

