### 6.2.3.5 Causality Relatedness to the IMP

The masked investigator will assess the causality/relationship between the IMP and the AE and record that assessment in the e-CRF based on the following definitions (only one answer possible):

Related: The AE is related to the tested product and cannot be reasonably explained by other factors (e.g., concomitant therapy, patient condition, and/or other intervention)

Not related: A simultaneous disease, a simultaneous treatment or any other known condition clearly triggers the AE.

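### At Visits #3, #4 and #5 the masked investigator is told the patient's compliance before making the slit-lamp grades and the tolerance rating, and the protocol gives no reason for that timing

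*Protocol*

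**What the plan says.** Protocol Section 6.1.2 introduces the Visit #3 procedures as "to be done according to the following order and in each eye by respecting the delegation of functions defined to maintain the masking". Visits #4 and #5 are introduced in the same way.

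The first block at each of these visits belongs to the unmasked team member. That person counts the returned product, "questions the patient on the IMP compliance (number of missing doses, if any, modification of instillation time"), and compares the answers with the diary. The block ends: "Information of compliance will be shared with masked investigator/designee employing a masked approach".

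The masked block follows. It covers symptoms, visual acuity, slit-lamp grades, IOP and adverse-event questioning, and then "Assessment of the efficacy and the ocular tolerance by the investigator". Patient status comes after these. Causality also rests with the masked side: "The masked investigator will assess the causality/relationship between the IMP and the AE" (Section 6.2.3.5).

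Section 5.1.4 (Masking) limits the hand-over. Compliance is to be shared "without revealing treatment allocation or type of IP". The same section adds: "The unmasked staff cannot help for any blinded procedures such as EDC entry".

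**The concern.** Patients know which product they use, because single-dose vials and bottles cannot be made to look alike (Section 3.2). The masked assessor is therefore the main safeguard for any outcome that rests on judgement. An assessor who has just heard that doses were missed may expect less redness, or less effect, before looking at the eye. Hiding the product does not remove that expectation.

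This would matter for a comparison of arms only if the compliance messages differ by arm. There are two plausible routes. Poor tolerability could cause missed doses. The returned-drug check is also finer for vials than for bottles. At stake are conjunctival hyperemia, ocular-sign scores, conjunctival and corneal staining, and the investigator's tolerance rating. These are tolerability data from a trial meant to inform Phase III (Section 3.2).

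**Working it through.** No figure in the plan depends on this point, and Section 7.5 declines a formal sample-size calculation, so there is nothing to reproduce. The check is mainly a reading of the text, followed by an illustration of size.

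**1. Order of events (Section 6.1.2).**

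| Step | Visits #3, #4, #5 |
|---|---|
| First block, unmasked | Count, interview, diary check, compliance passed to masked staff |
| Masked block | Symptoms, slit-lamp grades, IOP, AE questioning, investigator efficacy and tolerance ratings, patient tolerance rating |
| End of masked block | Patient status |

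The order applies at up to 126 × 3 = 378 visits. That is the number of hand-overs, not the number of biased scores.

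**2. What the masking rule covers.** Section 5.1.4 protects allocation and product type. It does not mention the number of missed doses, and the visible text gives no format for the message.

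**3. Whether the count is equally informative in each arm.** Section 5.1.3.1 supplies T4090 as 20, 20 and 30 vials, and Rhopressa as 1, 1 and 2 bottles. With on-time visits and one evening dose per day up to the day before the visit, the expected doses are 14 (Days 1–14), 14 (Days 15–28) and 21 (Days 29–49). One vial treats both eyes, so full compliance leaves:
- 20 − 14 = 6 vials at Visit #3
- 20 − 14 = 6 vials at Visit #4
- 30 − 21 = 9 vials at Visit #5

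Each further unused vial points to one missed dose. A bottle count cannot show this. The diary and interview apply in all arms, so they narrow the difference without necessarily removing it.

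**4. How much compliance alone could reveal about the arm.** The visible text gives no compliance figure by arm. Let *d* be an assumed standardised difference in reported compliance between T4090 (2/3 of patients) and Rhopressa (1/3), with normal distributions. Then AUC = Φ(d/√2). The best-guess accuracy is (2/3)Φ(c) + (1/3)[1 − Φ(c − d)], with c = d/2 + ln 2/d.

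| Assumed d | AUC | Correct guesses |
|---|---|---|
| 0 | 0.50 | 66.7% (always guess T4090) |
| 0.2 | 0.56 | 66.7% |
| 0.5 | 0.64 | 67.5% |
| 0.8 | 0.71 | 70.5% |

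Compliance says little about the arm unless the arms differ greatly.

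**5. Possible induced difference.** Suppose a rating moves *b* SD for each SD of reported compliance. The induced arm difference is b × d:
- d = 0.2: 0.1 × 0.2 = 0.02 SD; 0.3 × 0.2 = 0.06 SD
- d = 0.5: 0.1 × 0.5 = 0.05 SD; 0.3 × 0.5 = 0.15 SD
- d = 0: no difference

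Both *b* and *d* are assumptions.

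**6. Whether the hand-over must come first.** The protocol gives masked staff three uses for compliance. Non-compliance is listed among the discontinuation circumstances (Section 4.4.2). Missed and modified doses go into the e-CRF (Section 6.2.3.17), and unmasked staff may not enter data. AE reports include action taken with the product (Section 6.2.3.5.1). None of these needs the information before the eye is graded.

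**The case against.** The strongest reply has five parts.

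- **The hand-over is restricted and useful.** Section 5.1.4 bars revealing the allocation or product, and masked staff need compliance for the purposes above. This stands. A reader might infer that the sharing serves no need at all, but the documents do not support that. What is missing is a reason for the timing.
- **No arm difference is shown.** This also stands. A reader might infer that compliance is an arm-related fact, or that the message unmasks. Nothing in the documents says compliance differs by arm, and the illustration shows weak discrimination. The arm route is only possible.
- **Some judgements may properly use exposure.** Causality concerns relation to the product, and the efficacy question (Section 6.2.2.2) asks about the product's efficacy. Withholding missed doses could make these worse. This is a real trade-off, so the fix should not force either one ahead of the hand-over.
- **The order may be read too strictly.** The sharing sentence has no time word, Section 5.1.4 gives no timing, and staff roles are detailed in a delegation document that is not available. That is fair, but the sentence sits in the first block of a prescribed sequence, and sites may well follow it as printed.
- **The benefit is partial.** The same masked investigator sees the patient throughout (Section 3.2), so compliance from earlier visits is already known. This stands, and the change protects only against news of the latest interval.

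**Conclusion.** The point holds as a minor, avoidable weakness. At Visits #3, #4 and #5 the printed order gives the masked investigator missed-dose information before the slit-lamp grades and the tolerance rating, without explanation, and the masking rule does not cover the number of missed doses.

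The consequence is possible expectation bias in investigator-graded safety outcomes. The SAP (Section 17) makes no statistical comparisons on safety data unless otherwise specified. Under the assumed inputs the induced difference is 0.02 to 0.15 SD. It depends on reported compliance differing by arm and on the assessor reacting to it, and the documents establish neither.

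A reader might extend this to every subjective outcome or to the primary endpoint. That goes too far. The person applanating is masked to the tonometer readout and a second person reads it (Section 3.2), so IOP is largely protected. Patient-reported symptoms and tolerance come from someone who already knows which doses were missed.

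**What to change.** Leave the count and interview where they are. In Section 6.1.2, replace the sharing sentence at Visits #3, #4 and #5 with wording such as:

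*Compliance will be given to the masked investigator/designee in one common format (number of missed doses, no vial or bottle counts) only after this visit's slit-lamp scores, IOP measurements and investigator tolerance rating are recorded, and before patient status and e-CRF dosing entry.*

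- Add the same timing to the general rule in Section 5.1.4.
- Allow AE causality to be finalised after the hand-over and, if the sponsor wishes, the efficacy rating too. That would mean separating the efficacy rating from the tolerance rating, since they now share one line.
- Make the hand-over an explicit step at Visit #5, which has no later unmasked block.
- Make sure the common format also carries the other dosing fields that Section 6.2.3.17 requires, such as the last instillation.

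If the sponsor needs compliance first, the protocol should say why.

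The cost is a few sentences, with no new data or staff. The hand-over moves to the end of the visit day, after the 4:00 PM IOP, and knowledge from earlier visits remains.
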